9.2 ADMINISTRATION

EVG/COBI/FTC/TAF or EVG/COBI/FTC/TDF will be administered as one tablet orally once daily with food. Other ART regimens will be administered as per respective packet instructions.

9.3 DURATION

Participants will remain in the study through 2022 (about 5 years), regardless of time since HIV diagnosis and/or completion of the *Sabes* protocol. The visit weeks for MERLIN will continue to be counted with respect to HIV diagnosis/Sabes 3 enrollment. ART will be provided by the study for the duration of the time that the participant remains in the study. At the end of study, participants will continue ART from other sources, including transition to Peruvian MOH clinics.

9.4 STUDY PRODUCT FORMULATION AND PREPARATION

Elvitegravir/cobicistat/emtricitabine/tenofovir alafenamide (GENVOYA®) is co-formulated to contain 150 mg of elvitegravir, 150 mg of cobicistat, 200 mg of emtricitabine, and 10mg of tenofovir alafenamide in each tablet.

Emtricitabine/tenofovir DF (Truvada®) is co-formulated to contain 200 mg of emtricitabine and 300 mg of tenofovir DF and will be available when will be necessary to change the antiretroviral treatment.

Each bottle of the described medicaments contain a silica gel desiccant that should be kept in its original recipient to protect the product from humidity. The original recipient can be dispensed. Store at 25°C (77°F), variations from 15°-30°C (59°-86°F) are allowed.

9.5 PRODUCT SUPPLY

Co-formulated EVG/COBI/FTC/TDF (STRIBILD®) and EVG/COBI/FTC/TAF (GENVOYA®) will be provided by Gilead Sciences, Inc. Co-formulated emtricitabine/tenofovir DF (Truvada®) will be provided by Gilead Sciences, Inc. Truvada will be used only in combination with at least a third antiretroviral. Per discretion of the investigators, other drugs could be provided procured locally if one of the listed study drugs cannot be used.

9.6 PHARMACY FACILITIES

The pharmacy facilities are located at the IMPACTA Barranco and IMPACTA San Miguel Clinical Research Sites and both are staffed by registered trained pharmacists. Both pharmacies will have adequate space to store sufficient quantities of study agent to assure continuous access to all study participants. The study drug will be stored in accordance with the drug manufacturer's recommendations. Both pharmacies' storage and the study pharmacies will be locked by a secure door. The pharmacies and storage facilities have climate-controlled environments, with controlled humidity and temperature to remain within limits allowed by the manufacturer for drug storage.

9.7 DRUG INVENTORY

The pharmacists at the IMPACTA Barranco and IMPACTA San Miguel Clinical Research Sites will receive the study agent and store it in the pharmacy. Access will be restricted to authorized pharmacy personnel only. The pharmacists will be responsible for keeping accurate records of the material received. At the end of the study, the pharmacists will perform the final drug accounting of unused study material on the proper log documents. Unused study agent will be disposed of in accordance with local regulations.

9.8 DRUG DISPENSING

The Study Pharmacist will be responsible for dispensing the drug to the Study Nurse who will deliver it to the participant. At each visit, the pharmacist will receive the prescription that includes the participant's enrollment ID number. The pharmacist will dispense the drug according to the procedures shown in Figure 2. For bottle dispensed, the pharmacist will enter the packed label information and date in a Drug Dispensation Log, to be kept secure in the Pharmacy.

9.9 CONCOMITANT MEDICATIONS

To avoid adverse events caused by drug interactions, investigators must refer to the most recent package insert for study drug and concomitant agents whenever a concomitant medication is initiated or a dose is changed.

Research sites must also refer to the study product's most recent package insert or investigator brochure to access additional current information on prohibited and precautionary medications.

Below are lists of selected concomitant medications. These lists are only current as of the date of this protocol. Therefore, whenever a concomitant medication or study agent is initiated or a dose changed, investigators must review the concomitant medication's and study agent's most recent package inserts or investigator brochure to obtain the most current information on drug interactions, contraindications, and precautions.

9.9.1 Precautions with Concomitant Medications

Package inserts of antiretroviral drugs and concomitant agents should be referenced whenever a concomitant medication is initiated or a dose is changed to avoid drug interaction AEs.

9.9.2 Prohibited Medications

Co-administration with drugs that are highly dependent on CYP3A for clearance and for which elevated plasma concentrations are associated with serious and/or life-threatening events is contraindicated. These drugs and other contraindicated drugs (which may lead to reduced efficacy of STRIBILD and possible resistance) are listed in the table below.

Table 1a: Drugs that are Contraindicated with STRIBILD and GENVOYA

MEDICATION CLASS	PROHIBITED MEDICATIONS
ALPHA 1-ADRENORECEPTOR ANTAGONIST	Alfuzosin
ANTIMYCOBACTERIAL	Rifampin
ERGOT DERIVATIVES	Dihydroergotamine Ergotamine Methylergonovine
GI MOTILITY AGENT	Cisapride
HERBAL PRODUCTS	St. John's wort (Hypericum perforatum)
HMG-COA REDUCTASE INHIBITORS	Lovastatin Simvastatin
NEUROLEPTIC	Pimozide
PHOSPHODIESTERASE-5 (PDE5) INHIBITOR	Sildenafil when dosed as REVATIO for the treatment of pulmonary arterial hypertension
SEDATIVE/HYPNOTICS	Triazolam Orally administered midazolam

* Some brand names are showed, but attention must be taken about the generic name.

**A single dose of midazolam may be used for sedation in subjects undergoing procedures in a monitored setting.

9.9.3 Options for Medication Substitutions Due to Intolerance/Toxicity

If intolerance or toxicity occurs, substitutions may be made to the study regimen, after discussion with the Protocol Chair, as long as the new regimen is consistent with current guidelines for potent ART. The substituted medications will be provided by the study for the duration of time that the participant remains in the study. The purpose of the study is to determine whether ART in general, not necessarily a specific regimen, affects the long-term clinical benefit for MSM and TG with different alcohol consumption levels, who acquired HIV recently. However, because in this study we are performing additional analysis comparing treatments based on EFV and EVG, those participants undergoing these medicament substitutions could be excluded from such secondary analyses.

9.9.4 Options for Medication Substitutions for Virologic Failure

If a subject develops virologic failure on the study regimen further management based in clinical judgment should proceed at the discretion of the On-Site Principal Investigator in consultation with the Protocol Chair or Co-Chair.

Substitutions in antiretroviral regimens during the course of the study are at the discretion of the site investigator. It is the site investigator's responsibility to review all concomitant medications to ensure safety. The protocol pharmacist is available for discussion if questions arise.

The substituted medications will be provided by the study for the duration of time that the participant remains in the study.

9.10 ADHERENCE ASSESSMENT

Adherence will be assessed via validated self-report measures, pharmacy refill-based measures, and unexpected increases in HIV plasma viral load. Specifically, the Visual Analogue Scale [49] and the Ability Likert item [50] will be used to collect self-reported adherence over the past 30 days, collected monthly. These measures have demonstrated consistent associations with viral load in other studies [51]. Because self-report has a number of limitations, including a tendency of over-estimate adherence in comparison to electronic drug monitoring measures as well as potentially high demands on other cognitive processes to produce accurate reports [52], we also will monitor pharmacy dispensation records to produce medication possession ratios (days covered by a prescription/days between scripts) in approximately 3-month intervals. Pharmacy-based measures of adherence have consistently been associated with clinical outcomes in previous research [53, 54]. We will not monitor ART blood levels because 1) this is not done as part of routine clinical practice, 2) the tests would only refer to recent adherence rather than adherence over time, and 3) it is rather expensive to conduct these tests.

10. STUDY PROCEDURES

10.1 Visit Program

Procedures and Sample collection		Reference to Arm of ART initiation in SABES 3	ENR (Enrollment with acute infection diagnosis)	Study week +/- 28 days				ENR 3,4 (enrollment after SABES participation)	Study week (counted since enrollment into SABES study –after HIV diagnosis) +/- 8 weeks of window								Annual Visits		Bi-annual visits
				12	24	36	48		72	96	120	144	168	192	216	Every 48 weeks after wk 192 for the immediate arm (I)	Every 48 weeks after wk 216 for the deferred arm (D)		
Informed Consent	both	X						X											
Clinical Procedures ⁵	both	X	X	X	X	X	X	X	X	X	X	X	X	X	X	X	X	X	
Questionnaire (CASI)	both	X		X		X	X	X	X	X	X	X	X	X	X	X	X	X	
Pneurophsycologic test	both	X		X		X	X	X	X	X	X	X	X	X	X	X	X		
Abdominal circumference*	both							X	✓	✓	✓	X			X	X	X		
Stool	New ENR	Immediate	X		X		X		X	X	X	X	X	X	X				
	Collection in the past	both						X	X	X	X	X	X	X	X	X	X	X	
	No collection in the past	Immediate													X ¹				
		Deferred													X ¹				
Rectal biopsy and secretion (N=60)		Immediate							X		X		X						
		Deferred								X		X		X		X			
Urine	Both	X		X	X	X	X	X	X	X	X	X	X	X	X	X	X		

BLOOD																
ART safety tests (Biochemistry, liver function and hematology)	both	X		X		X	X	X	X	X	X	X	X	X	X	X
CD4/CD8	both	X				X	X	X	X	X	X	X	X	X	X	X
HIV viral load	both	X		X		X	X	X	X	X	X	X	X	X	X	X
Lipid panel**	both	X				X	X ²	√ ²	√ ²	√ ²	X			X	X	X
Glucose**	both	X		X		X	X ²	√ ²	√ ²	√ ²	X			X	X	X
PBMC	both	X		X		X	X	X	X	X	X	X	X	X	X	X
Plasma	both	X		X		X	X	X	X	X	X	X	X	X	X	X
Whole blood (RNA LATER)	both					X	X	X	X	X	X	X	X	X	X	

Procedures and sample collection	Reference to Arm of ART initiation in SABES 3	ENR (Enrollment with acute infection diagnosis)	Study +/- 28 days week				ENR 3, 4 (enrollment after SABES participation)	Study week (counted since enrollment into SABES study –after HIV diagnosis) +/- 8 weeks of window								Annual Visits		Bi-annual visits	
			12	24	36	48		72	96	120	144	168	192	216	Every 48 weeks after wk 192 for the immediate arm (I)	Every 48 weeks after wk 216 for the deferred arm (D)			
Leukapheresis (N=40)	Inmediato								X		X		X		X				
	Diferido								X		X		X		X		X		
Dried blood	ambos						X	X	X	X	X	X	X	X	X	X	X		
Syphilis tests	ambos						X	X	X	X	X	X	X	X	X	X	X		
Max volumen of blood (ml) Including leukapheresis (if applicable)	ambos	250		250		250	250	250	250	250	250	250	250	250	250	250	250	30	

✓ conditiona procedure X obligatory procedure

* The measurement must be taken the same day of simple collection for lipid panel and glucose

** fasting

¹ for those in which stool sample was not collected in the Sabes 3 enrollment visit, the sample must be taken in week 192 for the immediate arm participants and in week 216 for the deferred arm participants.

² the sample for lipid panel and glucose must be taken during fasting; however, if the participant is not fasting during the enrollment visit, the sample can be recovered in the immediately following visit.

³ If the enrollment visit occurs within 8 weeks after the Observational study “Collaborative Studies of the Effect of Very Early Initiation of ART and Development of HIV Incidence Assays in Lima, Peru”) visit, it will not be necessary to collect samples collected during such visit (PBMC, stool, urine); the only sample to be collected will be for safety test, CD4/CD8, viral load, lipid panel and glucose.

⁴ If the enrollment visit occurs within the window period of the week visits, 72, 96, 120, 144, 168, 192, 216 or the following every 6 month visits; then it will not be necessary to collect samples already obtained in the enrollment visit (PBMC, stool, urine) in the next follow-up visit; only a sample to run safety tests should be collected.

⁵ Medical chart evaluation, physical exam, concomitant medication and diagnosis will be performed.

⁶ For participants in the Group D and any other who did not have lumbar puncture before 2018, the lumbar puncture procedure will not be done in weeks 96/120, but only after week 144 (based on study arm).

⁷ The last lumbar puncture procedure will be done at week 240 for the immediate arm and week 264 for the deferred arm.

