Specimen collection: The MERLIN study involves laboratory analysis of specimens collected during the 48-week SABES study as well as during the MERLIN study, through 2022 (about 5 years after MERLIN enrollment). Visits with specimen collection occurred in the SABES study at 1, 2 and 4 weeks after ART initiation (study weeks 1, 2, 4 for the Immediate arm and weeks 25, 26, 28 for the Deferred arm); additional visits occur at 8, 16, 24, 32, 40 and 48 weeks. Extensive samples, including blood, stool for microbiome, and dried blood spots and hair for drug and alcohol tests were collected at each study visit for SABES study participants, starting at participant number 110. In addition, during the latter half of the SABES study, neurocognitive testing was conducted starting at participant 110, as well as collection of cerebrospinal fluid (CSF) by lumbar punctures on a subset to investigate the early neurologic impact of HIV infection. For the MERLIN study, we will collect blood, urine, rectal secretions and rectal biopsies, and stool specimens every 24 weeks throughout 2022, as well as additional neurocognitive testing and collection of CSF on a subset of participants.

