10.3 TIMING OF VISITS

10.3.1 Enrollment Assessments

10.3.1.1 Participants from SABES step 3

The enrollment into the MERLIN study can occur at any time after having completed SABES Step 3, including immediately after the final visit of SABES.

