10.3.2. Follow-up Assessments

10.3.2.1 Participants from SABES step 3

The MERLIN study visits should occur at 24-week intervals with respect to SABES enrollment, rather than with respect to MERLIN enrollment in order to preserve time-points with respect to date of SABES enrollment and ART randomization

If the participant received MOH-based ART after completing SABES, the study visit schedule should resume a 24-weekly schedule with respect to timing from SABES enrollment, at the next possible visit (e.g. 72, 96, 120, etc., weeks).

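### Footnote 4 of the visit table does not say which visit it waives; read literally, enrolling 0-8 weeks after a scheduled week leaves 40-48 weeks without PBMC, stool or urine

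*Protocol*

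**What the plan says.** The visit table in Protocol 10.1 sets follow-up at weeks 72, 96, 120, 144, 168, 192 and 216, each with plus or minus "8 weeks of window". Section 10.3.2.1 fixes the grid: "The MERLIN study visits should occur at 24-week intervals with respect to SABES enrollment, rather than with respect to MERLIN enrollment". Section 10.3.1.1 leaves the enrollment date open: "The enrollment into the MERLIN study can occur at any time after having completed SABES Step 3".

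Footnote 4 deals with overlap between enrollment and a scheduled visit. Its trigger is "If the enrollment visit occurs within the window period of the week visits, 72, 96, 120, 144, 168, 192, 216", or a later six-monthly visit. Its consequence is that "it will not be necessary to collect samples already obtained in the enrollment visit (PBMC, stool, urine) in the next follow-up visit"; at that visit "only a sample to run safety tests should be collected".

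Other text describes regular sampling. Section 7.1 states that "we will collect blood, urine, rectal secretions and rectal biopsies, and stool specimens every 24 weeks throughout 2022". Section 10.3.4.11 has PBMC stored at every time point, and the table marks PBMC and urine as obligatory at these weeks. Participants with earlier stool collection give stool at every visit (10.3.4.12).

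**The concern.** The trigger refers to one visit (the one whose window contains the enrollment) and the waiver to another (whichever comes next). These are the same visit only when enrollment precedes the nominal week. The footnote is evidently meant to avoid sampling someone twice for one time point, but its wording also reaches a visit 16 to 24 weeks later, where nothing would be duplicated.

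PBMC and stool supply the activation, reservoir and microbiome primary endpoints (14.3.1). Section 6.1 compares the groups at matched times since ART start, and Amendment Letter 3 places evaluation of the main objectives at years 2 and 4 of ART. A specimen that was not drawn cannot be recovered at the analysis stage.

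**Working it through.** **Inputs.** Visit spacing: 24 weeks from SABES enrollment (10.3.2.1). Window: 8 weeks either side (10.1). Enrollment date: any time after SABES Step 3 (10.3.1.1). The protocol states no gap figure to reproduce.

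**Notation.** Enrollment is at week W + e, where W is a scheduled week and e lies between -8 and +8.

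**Literal reading.** The waived visit is the next nominal week: W if e < 0, and W + 24 if e ≥ 0. The next collection comes 24 weeks after the waived visit.
- e < 0: gap = (W + 24) - (W + e) = 24 - e
- e ≥ 0: gap = (W + 48) - (W + e) = 48 - e

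**Same-window reading.** The waived visit is always W, so the gap is 24 - e throughout.

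With W = 72:

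| Enrollment week | Waived (literal) | Next collection (literal) | Gap, literal | Gap, same-window |
|---|---|---|---|---|
| 64 | 72 | 96 | 32 | 32 |
| 71 | 72 | 96 | 25 | 25 |
| 72 | 96 | 120 | 48 | 24 |
| 73 | 96 | 120 | 47 | 23 |
| 76 | 96 | 120 | 44 | 20 |
| 80 | 96 | 120 | 40 | 16 |

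The readings agree before the nominal week and differ by 24 weeks from it onward: 40-48 weeks against 16-24. If the next collection visit uses its own +8 weeks, the literal maximum becomes 48 + 8 = 56 weeks.

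**Comparison with footnote 3.** That footnote waives samples only when enrollment falls within 8 weeks after an Observational Study visit, and only those taken at that visit. Footnote 4, read literally, waives samples due 16-24 weeks after enrollment.

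**Which analysis points are touched.** Taking 52.18 weeks per year and ART start at week 0 (Immediate arm) or week 24 (Deferred arm):
- Year 2: 2 × 52.18 = 104.4, so about week 104 (Immediate) and 104.4 + 24 = 128.4, about week 128 (Deferred). The nearest scheduled visits are week 96 (8.4 weeks away, against 15.6 for week 120) and week 120 (8.4 weeks, against 15.6 for week 144). The literal rule removes week 96 for Immediate participants enrolling at weeks 72-80, and week 120 for Deferred participants enrolling at weeks 96-104.
- Year 1.5: 1.5 × 52.18 = 78.3, so about week 78 (Immediate) and 78.3 + 24 = 102.3, about week 102 (Deferred). Those same participants have enrollment samples at weeks 72-80 and 96-104, which span these points.

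**The case against.** The strongest reply is that the footnote is only loosely worded. The week-72 visit stays open until week 80, so for someone enrolling at week 76 it can still be the visit that comes next. A trigger based on the window makes sense only as a rule against duplicate sampling within it. The instruction in 10.3.2.1 to resume "at the next possible visit (e.g. 72, 96, 120, etc., weeks" does not settle the matter: it concerns participants who received Ministry of Health ART after SABES, and week 72 is still possible at week 76. The first clause of the waiver is also permissive. All of this stands as evidence of intent. But the footnote does not say it, its last clause directs that only a safety sample be taken, and two sites could apply it differently.

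A reader might infer three stronger things that the documents do not support.

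- **A count.** If enrollment were spread evenly, 8/24 = one third would fall after a nominal week, or 75 of the 225 enrolled in SABES by March 2016. The protocol gives no enrollment times and does not show that all 225 joined MERLIN. Sections 8.2 and 10.2.1 provide for transfer around week 48, before the first listed window opens at 72 - 8 = week 64. Under footnote 3 some participants give no PBMC, stool or urine at enrollment, and footnote 4 waives only what enrollment obtained. Those without earlier stool collection give one late sample only, so serial stool is not at issue for them.
- **Loss of the first long-term assessment.** At the 1.5 years set in 4.1 and 6.1, the enrollment sample generally serves, as shown above. The concern applies to year 2.
- **Loss of participants from the comparison.** They lose one collection and keep the enrollment sample and later visits. Leukapheresis is not among the waived items.

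**Conclusion.** The point holds as a defect in a stated collection rule. Footnote 4 does not identify the waived visit, and its literal reading gives a nominal gap of 40-48 weeks instead of 16-24 for anyone enrolling 0-8 weeks after a scheduled week. That contradicts the 24-weekly collection in 7.1 and PBMC storage at all time points in 10.3.4.11. It can remove the visit nearest year 2 of ART in either arm.

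The gap follows from the protocol's own spacing and window and needs no assumption about enrollment patterns. It does depend on sites reading the next visit as the next nominal week. How many participants are affected cannot be derived from the protocol. For stool, only those with earlier collection are exposed. For PBMC, the point matters only up to week 192 (Immediate) or 216 (Deferred) once Amendment Letter 3 applies, because that letter ends PBMC collection afterwards.

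**What to change.** Reword footnote 4 to say that, when enrollment falls within the window of a scheduled visit, the enrollment samples count as that visit and are not repeated for it, and that the following scheduled visit is sampled in full as the table requires.

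For participants already handled otherwise, label the enrollment sample with the week whose window contains it, so that it enters the analysis at the right time since ART start. Specimens already missed cannot be restored.

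The cost is one footnote and a note to sites. It adds no sampling beyond what the visit table already asks for.

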10.2 RECRUITMENT

10.2.1 SABES 3 Participants

SABES 3 Participants will be recruited from current SABES study participants at any time during SABES 3 follow-up, immediately after the week 48 visit, or after they have entered follow-up care at IMPACTA or TARGA Clinical sites.

10.2.2 New participants with acute infection

Up to 25 new participants with acute hiv infection will be enrolled. The diagnosis will be done during the acute phase of HIV infection (positive HIV RNA test or p24 antigen with negative HIV antibody test) at the IMPACTA site or other collaboration institutions. These participants will rapidly be referred to this study.

10.3 TIMING OF VISITS

10.3.1 Enrollment Assessments

10.3.1.1 Participants from SABES step 3

The enrollment into the MERLIN study can occur at any time after having completed SABES Step 3, including immediately after the final visit of SABES.

10.3.1.2 New participants with acute HIV diagnosis

The new participants entering with acute HIV diagnosis will be enrolled as soon as possible after HIV diagnosis.

10.3.2. Follow-up Assessments

10.3.2.1 Participants from SABES step 3

The MERLIN study visits should occur at 24-week intervals with respect to SABES enrollment, rather than with respect to MERLIN enrollment in order to preserve time-points with respect to date of SABES enrollment and ART randomization

If the participant received MOH-based ART after completing SABES, the study visit schedule should resume a 24-weekly schedule with respect to timing from SABES enrollment, at the next possible visit (e.g. 72, 96, 120, etc., weeks).

